APPENDIX: VIDEO/TELEHEALTH VISIT ADDENDUM TO SWITCH STUDY

Video/telehealth Standard Practices

- Throughout the modified protocol, MyChart/CareConnect Video will be the preferred platform that will be used. In the event that this platform fails, we will follow current UCLA Health System guidance and use currently approved patient-facing platforms. If no video platforms work, we will use telephone only. If telephones do not work, we will reschedule the visits as needed.
- We will use standard video/telehealth practices including verifying identity, privacy, location, emergency contact information, in case of emergency.

Inclusion/Exclusion criteria:

Inclusion criteria: same as previously approved protocol with one addition. The participant must be:

- “Available to attend weekly in-person or video sessions over 9 weeks”

Exclusion criteria: No changes

Recruitment

Step 1 (identification of participants): No changes

Step 2 (screening for current or prior insomnia and current hypnotic use

Telephone screening:

No changes except--Following completion of the telephone screening questionnaire, eligible and interested individuals will be scheduled for an initial meeting to obtain written informed consent. An email address or mobile number will be requested at the end of the screening visit.

Patient preference for social/physical distancing

Following completion of the screening questionnaire, eligible and interested patients will be asked whether they prefer “Always In-Person” visits (**AIP**) versus “Sometimes In-Person” visits (**SIP**), which will entail picking-up/dropping-off of study material/equipment in-person versus “Never In-Person” visits (**NIP**, all study materials transported via mail/delivery services). Individuals who opt for AIP will follow the approved in-person protocol.

AIP=Patient prefers Always In-Person contact with study team

SIP=Patient prefers Sometimes-In-Person contact with study team. Specifically, video visits for assessments and intervention, but is willing to pick up and drop off study material

NIP=Patient prefers Never In-Person contact with study team. All contact is remote/virtual.

Step 3: Consent visit

Video consent option for SIP and NIP

Patients will be offered a video visit as an alternative to an in-person consent visit. A UCLA Health System approved video visit platform (e.g., Care Connect Video Visit) will be used. The same procedures used for the in-person consent visit will be used for the video visit.

The same staff that conduct the in-person consent visit will conduct the video visit.

- Preparation for consent appointment:

- Auto-generated appointment reminder in CareConnect will be sent for CareConnect video visit.
- Research staff will email/text instructions for the appointment, appointment date/time, copy of enrollment/consent documents (e.g., informed consent form, UCLA HIPAA form, participant list of rights, etc.).

- Research staff will deliver (mail/courier/delivery service) a cover sheet describing the contents of the delivery, enrollment/consent documents, self-addressed, postage paid return envelope, paper disposable ruler (needed for assessment visit to obtain neck circumference)
- Return of study materials
 - Patients who electronically sign enrollment/consent documents (e.g., informed consent form, HIPAA forms) will email the signed forms back to the research staff. We will follow UCLA Health System Compliance and IT guidance and will only use approved electronic signature software, if and when they become available.
 - Patients who sign hard copies of the consent and HIPAA forms will mail the signed forms back in the return envelope.

Step 4 Baseline assessment to determine remaining eligibility criteria: After participants have provided written informed consent, they will complete a baseline assessment that consists of 2 visits (each 45-60 minutes).

Baseline Visit Procedures

1) Version for SIP participants

- At the beginning of the Baseline 1 visit, staff will instruct participant that they need a blank piece of paper and pen. The research assistant will administer questionnaires in original protocol, except Trails and Digit Symbol/Symbol Copy, which will be moved to Baseline 2 visit. The RA will show the responses to questionnaires.
- Research staff will document the responses in electronic format or hard copy and store the copies in the approved research servers or office spaces.
- At the end of the Baseline 1 visit, the research staff will arrange for in-person pick-up of materials

Pick-Up of Baseline materials:

- A wrist actigraph will be given to participants to wear at home for 1 week
- A sleep diary will be given to participants to complete while wearing the actigraph
- If a participant scores > 4 on the STOP-Bang and does not have documentation of a previous sleep study in the medical record, s/he will be sent home with an Food and Drug Administration-approved portable sleep apnea screening device (e.g., WatchPAT, NoxT3, Alice NightOne) to wear for one night. The sleep study will be interpreted by a board-certified sleep medicine physician on the research team (e.g., [name], [name]). The participant will return the device the next day to the research office.
- Hypnotic medication log - Using a structured hypnotic abstraction form (see Hypnotic Abstraction Form), we will review the UCLA medical record to obtain data about hypnotic prescriptions. We will also query the California Controlled Substance Utilization Review and Evaluation System (CURES) database to obtain data about prescriptions of controlled substances.
- Paper copies of the Trails, Digit Symbol/Symbol Copy will be included in the packet to be used at the video Baseline 2 visit
- Other baseline assessment forms/instructions
- “Return Delivery” packaging to be used when returning materials to research office

2) Version for NIP participants

- At the beginning of the Baseline 1 visit, staff will instruct participant that they need a blank piece of paper and pen. The research assistant will administer questionnaires in original protocol, except Trails and Digit Symbol/Symbol Copy, which will be moved to Baseline 2 visit. The RA will show the responses to the questionnaires video or by sharing desktop.
- At the end of the video appointment, the research staff will arrange for delivery of study materials.

Delivery of Baseline materials:

- A wrist actigraph

- Sleep diary
- Trails and Digit Symbol/Symbol Copy to be used at video Baseline 2 visit
- If STOP-BANG > 4, then portable sleep apnea screening device (e.g., WatchPAT, NoxT3, Alice NightOne)
- Hypnotic medication log
- Other baseline assessment forms/instructions
- Postage-paid, pre-addressed, insured delivery packaging (“Return Delivery” packaging)

In both the SIP and NIP patients, the One-leg Balance will be omitted due to the need for physical contact to safely perform this test.

MINI: As needed video MINI appointment: If a MINI is needed, a separate video MINI visit with a staff trained in administering the MINI will be arranged and preparatory emails will be sent to the participant.

Eligibility determination for randomization

No change

Randomization

No change

Interventions

No change to content of sessions

Preparatory emails to schedule each video intervention session (automated email and emails from interventionist to patient confirming video appointments—the list of emails may be combined in one email and during the intervention, changes to video appointments will be made either by corresponding with the participant or via email)

Getting Materials/Medications to Randomized Participants:

1) Version for SIP Participants

- Pick Up of materials prior to session 1:
 - Notebook of content for weeks 1 to 9 (last week’s content omitted)
 - Diaries for all weeks
 - Blood pressure cuff (if participant does not have one)
 - CIWA, ISI, ESS questionnaires (in sealed envelopes, labeled for each session)
 - Medications for MTcap: 3 week supply plus 3 weeks PRN plateau
 - Medications for SGT: 1 bottle (no change) plus Paper Taper Schedule and pill cutter in a sealed envelope to be opened at Session 1 (no change to content of taper schedule)
 - Extra copies of forms/instructions
 - Postage-paid, self-addressed return envelopes
- Pick Up of meds at Day 14
 - Medications for MTcap: 3 week supply plus 3 weeks PRN plateau
- Pick Up of meds at Day 28
 - Medications for MTcap: Remaining 2 weeks supply plus 2 weeks PRN plateau
 - Box for returning materials at the end of sessions
- Delivery of final session content material will be timed to occur with “session 8 content”

2) Version for NIP Participants

- Similar to SIP schedule above, except that delivery of materials/medications will occur in lieu of in-person pick up.

Measures collected during video visit intervention:

- Urine
 - SIP—a urine sample will be collected from participants between the randomization time point and the first intervention session. The urine sample will be tested for benzodiazepines and zolpidem to confirm the participant's use/nonuse of these hypnotics.
 - NIP—We will offer to mail a urine specimen collection container to the participant and to pick it up via UCLA-approved courier service to bring the specimen back to the UCLA lab in CHS that processes research specimens.
- Questionnaires: Weekly throughout the intervention for participants in both study groups the participant will complete the items and show the completed instruments to the interventionist. If necessary, the interventionist may administer the items verbally.
 - Clinical Institute Withdrawal Assessment Scale - Benzodiazepines (CIWA-B): This 22-item instrument includes patient symptoms and clinical observations (e.g., tremor) to assess and monitor the type and severity of symptoms of benzodiazepine withdrawal.
 - Vital signs: These physical examination measurements will be self-reported by participants weekly: blood pressure, pulse.
 - Insomnia Severity Index (ISI): The ISI is a 7-item instrument that measures perceived severity of insomnia symptoms (total score ranges from 0 to 28).
 - Epworth Sleepiness Scale (ESS): This 8-item questionnaire assesses general level of daytime sleepiness.
 - Daily sleep and habits diary: No change. The interventionist will look at the diary on the screen/camera.

Video visit Hypnotics Taper and CBTI-augmented program

- 1) MTcap (Masked Taper plus cognitive behavioral therapy-augmented program): Hypnotic taper protocol: No change to tapering rate. The interventionist will confirm with the participant at the end of each video session the blister pack that will be taken for that week. Cognitive behavioral therapy for insomnia-augmented program: No change
- 2) SGT+CBTI: No changes

Video Visit Extended taper plan: We have identified specific situations when the taper plan may need to be modified:

- 1) Withdrawal symptoms/extended taper required: In the MTcap video group, an extended taper may be achieved by instructing the participant to open the sealed envelope containing the duplicate 7-day blister pack (e.g., plateauing the doses until the participant is ready to move to the next blister pack), showing it to the interventionist and instructing the participant to take it that week. In the SGT+CBTI group, participants will be instructed to repeat a particular week in the printed taper schedule. If necessary, additional study medication will be delivered/picked up by the participant if the participant requires extended plateau or needs additional medication (e.g., participant loses medication).
- 2) Hypnotic dosed as "prn" at baseline: No change to approved protocol.
- 3) More than 1 hypnotic at baseline: No change to approved protocol.

Video Visit Protocols for preparation of hypnotics

- 1) MTcap group: No change. The date of pick-up/mail date will be documented in the drug accountability log.

SGT+CBTI group: No change. The date of pick-up/mail date will be documented in the drug accountability log.

Protocols for distribution of hypnotics

A chain of custody will be established and documented. Only authorized members of the research team will be permitted to have contact with the medications. A delegation log will be maintained. For both groups, a member of the research team will pick-up the medication bottle or blister packs from the UCLA Research Pharmacy. The medications will be distributed according to the method described above (either pick-up or mailed versus social distancing preferences).

Care coordination at end of intervention period

No change

Follow-up assessments

The post and 6-month assessments will be conducted via video visits for SIP and NIP participants. Procedures similar to the approved in-person protocol will be followed with the following exceptions that will allow for social distancing:

Post-treatment assessment

Preparatory Emails

- (Auto-generated email): A reminder appointment email will be created and invitation for video Post 2 appointment will be sent to the patient
- (Research staff-generated email)
 - Participants will be emailed a confirmation of their Post 2 visit appointment
 - Participants will be provided instructions for preparing for the Post 2 assessment (e.g., anticipated duration, equipment/materials needed, staff contact information)

Getting Materials/Equipment to Participants

- 1) Version for SIP Participants will be advised to pick up Post assessment visit 1 materials (in sealed envelopes) 1 day prior to session 8 and to go to the lab to give urine sample (urine tox and urine zolpidem)
 - Diary
 - Questionnaire packet/instructions
 - Medication log
 - Fall log
 - Wrist actigraph
 - Return Box
- 2) Version for NIP Participants will be mailed Post materials a few days before session 8
 - Diary
 - Questionnaire packet/instructions
 - Medication log
 - Fall log
 - Wrist actigraph
 - Urine specimen container
 - Postage-paid return, insured Return Box

As with the original AIP protocol, the post-treatment assessment will begin on the same day that the participant completes session 8 of either intervention. At the end of session 8, a participant will be instructed to put on the actigraph to wear at home for 1 week and to complete the sleep and medication diary. When the participant returns the actigraph and diary after 1 week, he/she will be administered selected questionnaires included in the baseline assessment. Participants will also be instructed on the six-month fall log to record any falls they experience during the period between the

post-assessment and the six-month follow-up assessment. A courier will be sent to pick up the urine specimen and will deliver it to the UCLA lab in CHS that processes the research labs.

Six-month follow-up

Preparatory Emails

- (Auto-generated email): A reminder appointment will be created and invitation for 6-month follow-up appointment will be sent to the patient
- (Research staff-generated email)
 - Participants will be emailed a confirmation of their 6-month follow up visit appointment
 - Participants will be provided instructions for preparing for the 6-month follow up (e.g., anticipated duration, equipment/materials needed, staff contact information)

Getting Materials/Equipment to Participants

- Version for SIP Participants will be advised to pick up 6-month follow up visit 1 materials (in sealed envelopes) 1 day prior to 6-month follow up and to go to the lab to give urine sample (urine tox and urine zolpidem)
 - Diary
 - Questionnaire packet/instructions
 - Medication log
 - Wrist actigraph
 - Return Box
- Version for NIP Participants will be mailed 6-month follow up materials a few days before session 8
 - Diary
 - Questionnaire packet
 - Medication log
 - Wrist actigraph
 - Urine specimen containers
 - Postage-paid return, insured Return Box

A courier will be sent to pick up the urine specimen and will deliver it to the UCLA lab in CHS that processes the research labs.

Incentives for study participation

No changes.

Follow-up for Missed Appointments

No changes.

Benefits and Risks

no changes.

Primary data analysis plan and power analyses

No changes

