SGT+CBTI group: [name] or [name] will write prescriptions for the appropriate hypnotic that will cover the entire intervention period. The prescriptions will be sent via encrypted email or fax to the pharmacy. The compounding pharmacy will prepare a 30-day supply of the appropriate medication for the participant. The medication will be dispensed in a regular prescription bottle and labeled by the pharmacy. At the end of the month, a second 30-day supply of medication will be prepared and dispensed. The medication will be sent via overnight mail or courier to the UCLA Research Pharmacy. If necessary, the medications will be picked up by research staff and transported to the Research Pharmacy. The medication information will be entered into CareConnect (not as an active order) as “[medication name] study material Week [enter#]”.

Protocols for distribution of hypnotics

A chain of custody will be established and documented. Only authorized members of the research team will be permitted to have contact with the medications. A delegation log will be maintained. For both groups, a member of the research team will pick-up the medication bottle or blister packs from the UCLA Research Pharmacy upon arrival of the participant to the UCLA site and give it to the participant at the appropriate intervention session (for the SGT+CBTI group, at the initial session; for the MTcap group, at each intervention session). In the rare case that a participant reschedules the appointment after the medication has been dispensed, the medication will be temporarily stored in a safe. In the rare case that a patient withdraws from the study after the medications have been dispensed from the research pharmacy, the medication will be disposed of following US Drug Enforcement Agency Public Controlled Substance Safe Disposal protocol (e.g., in a DEA authorized collection bin, with two witnesses signing the chain of custody log).

For participants seen at off-campus sites, a research team member will transport the medication via personal car from the UCLA Research Pharmacy to the off-campus site. The medication will be placed in a locked bag and stored in the trunk during transport. The medication will be stored in a locked safe at the off-campus location until the participant receives it at the first session. If the participant does not come to the appointment, the medication will be returned to the safe.

Care coordination at end of intervention period

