
Confusion about duplicate hypnotic prescriptions: Participants may not understand that the hypnotic provided by the study (in blister packs or medication bottle) replaces the hypnotic that they were previously taking. This could result in participants taking both prescriptions at the same time, which would result in a higher dose than prescribed, and possible side-effects (e.g., daytime sleepiness, dizziness). To avoid confusion about duplicate hypnotic prescriptions, participants in both groups will be asked to bring all their medications to the first intervention session. The interventionist will identify the hypnotic that will be tapered and will place the bottle in a zip-locked plastic bag with a secure plastic tie. A label will be affixed to the outside of the plastic bag that states, "Do not take this medication during the 9-week SWITCH study unless instructed by the study staff." The interventionist

will explain that the participant will receive the same hypnotic either in a new medication bottle or in the blister packs and should put the old prescription in the plastic bag in a safe location.

Increased daytime sleepiness: Adjustments to the participant's sleep habits may result in some initial daytime sleepiness. Daytime sleepiness will be monitored during each weekly in-person intervention assessment with the Epworth Sleepiness Scale, and participants with increased daytime sleepiness will be counseled on the possibility of impaired cognition and increased fall and motor vehicle crash risk. If excessive daytime sleepiness is thought to be due to study-related sleep restriction (as opposed to, for example, a newly-prescribed medication from the individual's physician), the prescribed sleep schedule will be adjusted.

Mental discomfort: The minor risks associated with completion of the questionnaires include tediousness, fatigue, and/or mental discomfort answering the items. Participants could also find wearing the actigraph and WatchPAT device to be annoying or uncomfortable. To reduce the risk of mental discomfort among participants, research staff will be trained to recognize discomfort in participants, and they will be trained to remind participants of the voluntary nature of the research and the option for participants to decline participation in any portion of the research project.

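### The bag-and-label safeguard against taking the old and study hypnotics together has no remote version in the telehealth addendum, which leaves Benefits and Risks unchanged

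*Combined protocol and SAP*

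**What the plan says.** In the main protocol, Benefits and Risks has a paragraph on confusion about duplicate hypnotic prescriptions. It recognises that a participant may take the old and the study supply together, and so take more than prescribed, with possible sleepiness and dizziness. The control is that "participants in both groups will be asked to bring all their medications to the first intervention session". There the interventionist "will identify the hypnotic that will be tapered and will place the bottle in a zip-locked plastic bag with a secure plastic tie". The bag is labelled "Do not take this medication during the 9-week SWITCH study unless instructed by the study staff". The interventionist also explains that the study supply replaces the old one and that the participant "should put the old prescription in the plastic bag in a safe location".

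Under Protocols for distribution of hypnotics, staff collect study drug "upon arrival of the participant to the UCLA site and give it to the participant at the appropriate intervention session". For the SGT+CBTI arm this happens at the initial session, and for MTcap at every session.

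The telehealth addendum keeps the in-person protocol only for participants who choose always to attend in person (AIP). SIP participants have video sessions but collect and return materials in person. NIP participants have no in-person contact. If every video platform fails, the visit is by telephone. For SIP the supply step is headed "Pick Up of materials prior to session 1", and it includes "Medications for MTcap: 3 week supply plus 3 weeks PRN plateau" or, for SGT+CBTI, one bottle. NIP participants get the same by delivery. Session content is declared unchanged, and the closing entry reads "Benefits and Risks no changes".

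**The concern.** The safeguard sits inside the section that the addendum leaves untouched, but its central act needs the interventionist and the bottle in the same room. With SIP and NIP participants they are not. The addendum provides no substitute, and it also alters the order of events, so that study drug is already at home when the explanation is given.

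What is at stake is participant safety. The protocol itself identifies the hazard, and participants are older than 55. The addendum adapts other hands-on steps: it sends a paper ruler for neck circumference, provides a blood pressure cuff where needed, and drops the one-leg balance test. That suggests this step was overlooked, not deliberately dropped.

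**Working it through.** No formula or stated figure applies. The check sets each part of the safeguard against the addendum.

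| Part of the safeguard (Benefits and Risks) | In person | SIP / NIP under the addendum |
|---|---|---|
| All medications brought to Session 1 | Brought to the site | Can be shown on camera; not stated. No visual check by telephone |
| Old hypnotic identified | By the interventionist | Possible by video, since session content is unchanged |
| Bottle bagged and tied | By the interventionist | Not possible as written; no bag or tie listed |
| Label fixed to the bag | At Session 1 | No label listed |
| Explanation that study drug replaces the old supply | At Session 1 | Carries over |
| Study drug reaches the participant | At the session | Before Session 1 |

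**Materials.** The pre-Session 1 list under Getting Materials/Medications to Randomized Participants covers the notebook, diaries, blood pressure cuff, questionnaires, medications for each arm (with taper schedule and pill cutter for SGT+CBTI), extra forms and instructions, and return envelopes. The contents of the forms and instructions are not itemised, so a printed label might be among them, but the text does not say so, and a bag and tie are not forms.

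**Timing.** In person, no study drug is at home before Session 1. Remotely, an MTcap participant may hold 3 scheduled + 3 plateau = 6 weekly packs by then, and an SGT+CBTI participant one bottle. The plateau packs are in sealed envelopes (Video Visit Extended taper plan), and the SGT+CBTI taper schedule and pill cutter are sealed until Session 1. The text does not clearly say the same of the scheduled MTcap packs or the SGT+CBTI bottle. The interval between receipt and Session 1 is not given.

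**Bound on the dose.** The exclusion criteria cap the baseline dose at 8 mg/night diazepam-equivalent. The week-1 study dose is not stated as a percentage of baseline, so I assume 75% to 100%. A participant at the cap who took both supplies in full would then take 8 + 6 = 14 to 8 + 8 = 16 mg/night in week 1. This is an illustration only; the documents give no rate of double use.

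**What remains for remote participants.**
- Identification and explanation by video.
- Weekly Epworth Sleepiness Scale and CIWA-B.
- The 8 mg/night cap.
- Exclusion of people who cannot store study medication securely.
- Notice to the UCLA prescriber before randomization, with the prescriber able to refuse the taper.

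Weekly confirmation of the MTcap pack and the drug accountability log also continue, but they govern study drug and not the old bottle.

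**The case against.** The strongest reply is that leaving Benefits and Risks unchanged keeps the duty in force. Read with the unchanged session content, the study must still identify the old hypnotic, explain the replacement and have the bottle set aside; only the remote mechanics are unwritten. For SIP, staff could also seal the bottle, or hand over the bag and label, at the in-person pick-up.

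Much of this stands. A reader might infer that the addendum waives the safeguard; it does not. For SIP the step is unspecified and not impossible. But the addendum does not ask participants to bring their medications to the pick-up or place the interventionist there, and NIP participants have no such contact. A duty kept on paper without the materials or a method is likely to be met unevenly.

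A reader might also count the whole taper as added exposure to two supplies at home. The documents do not support that. In-person participants also take the bagged bottle home and keep it there with the study drug. The bag is a reminder and not a lock, so over the taper the contrast is a labelled, sealed bottle against one that may be neither. The only added time with both supplies at home is the interval before Session 1.

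**Conclusion.** The point holds as a procedural safety gap: a stated control for a named risk cannot be carried out as written when Session 1 is by video or telephone, and the addendum supplies neither the materials nor a substitute. It touches both arms. It is clearest for NIP and weaker for SIP.

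The loss is the labelled reminder, the supervised sealing, and a short period of unstated length with both supplies at home before the explanation. Given the controls that remain, the residual risk is modest. The share of participants choosing SIP or NIP is not stated, but the conclusion does not depend on it.

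A reader might go further and infer bias in hypnotic discontinuation (H2a) or hypnotic use (H2b). Nothing in the documents shows that double use would occur often or differ between arms, so no effect on any endpoint or on power is claimed. I class this as a cheap improvement.

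**What to change.** 1. In the addendum, under Getting Materials/Medications to Randomized Participants, add to the pre-Session 1 materials for SIP and NIP a zip-lock bag, a tie and the label printed with the wording already in Benefits and Risks. Include a note not to open study medication until Session 1.
2. State the remote procedure. At Session 1, before any study dose, the participant shows all medication bottles on camera, or reads out the labels if the session is by telephone, then seals and labels the old hypnotic under the interventionist's direction. If the session was by telephone, sealing is confirmed at the next video contact.
3. Under Benefits and Risks in the addendum, replace the no-change entry with a pointer to these steps.

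The cost is one bag, tie and label per remote participant and a few minutes at Session 1. Sample size, visit schedule, taper and outcomes are unaffected.
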